After patients make a decision about parent trial enrollment, we will debrief patients consenting to the parent trial about the random assignment of the incentives. The study will have adequate power to rule out between incentive size and risk perception (i.e., undue inducement) and between incentive size and income or economic well-being (i.e., unjust inducement), using formal "non-inferiority" tests, interactions. We also will explore potential benefits of incentives, such as the possibilities that incentives improve informed consent by making people attend more thoroughly to research risks, and that they expedite recruitment enough to be cost-saving on balance.

2. Background and Significance

Recruitment problems often cause randomized clinical trials (RCTs) to fail or accrue excess costs

The concomitant problems of under-enrollment and selective enrollment in randomized clinical trials have long plagued efforts to evaluate new and existing medical interventions. ⁹⁻¹³ For example, a recent Institute of Medicine report found that 40% of cancer RCTs are never completed and published.¹⁴ Under-enrollment occurs when too few research participants are enrolled to provide adequate statistical power to answer the study's primary research question. Because under-enrollment yields unacceptably high probabilities for type II (false negative) errors, these problems reduce the RCT's ability to answer the

research question, thereby degrading the trial's scientific value and hence, ethics.^{15,16} Selective enrollment occurs when certain subgroups within the target population enroll in proportions greater or less than their representation in that population. By limiting the generalizability of the trial's results, this problem also curtails scientific value.¹⁷

These problems typically arise due to unexpected impediments to participant recruitment, which has been called "the most difficult and challenging aspect of clinical trials.¹⁸" Even when investigators enroll an adequate number of participants, they rarely do so on schedule,^{13,19,20} or in a manner that attracts the full range of eligible participants.^{17,21} Further, participant recruitment represents one of the largest costs of conducting clinical trials, requiring an average of 13 hours and \$500 per subject in cancer trials at academic medical centers.²²

Financial Incentives may augment the precision, generalizability, and efficiency of RCTs

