The target enrollment of 576 patients in each RETAIN sub-trial was determined based on the primary goal of ruling out the possibility that incentives represent an undue inducement. Statistically, the presence of an undue inducement is represented by the interaction term between incentive amount and risk on the outcome of enrollment in the parent trial. Thus, we seek to rule out the possibility that the odds ratio associated with this interaction term is appreciably greater than a null value. To facilitate such a power estimation, we considered groups of participants with greater or less than the median level of risk perception who will be randomized to the highest incentive versus the lowest incentive. With an overall sample size of 576 participants in each parent study involved in the RETAIN trial, we assumed that 192 participants would be randomized to each of the 3 incentive arms. Assuming that randomization balances the incentives distribution within each risk-perception group, 96 participants will be assigned to each of the 3 incentives within both the high and low risk-perception groups. Among patients assigned to receive \$0, we set the OR contrasting the odds of enrollment between riskperception groups to 1, such that the OR for those assigned to receive the highest incentive (\$300 or \$500, in MOVE IT and BASC, respectively) represents the interaction odds ratio. We assume a true interaction OR of 1, and use a one-sided significance level of 0.0427 such that the upper 95.73% confidence limit on the observed OR falls entirely below the non-inferiority threshold. If the enrollment rate in the parent trials is 50%, we will have at least 80% power to rule out undue inducement, as represented by an interaction odds ratios of 2.0 or greater. However, because we will actually analyze risk as a continuous variable and incentive size as a 3-level variable, our true power will be greater than the estimates reported here. Similar analyses suggest similar levels of power to rule out the unjust inducement interaction terms.

8. Data Safety & Monitoring Board (DSMB)

We have chartered a DSMB to monitor RETAIN, with purview over both embedded trials, for the expressed purpose of evaluating evidence of undue or unjust inducement. Any serious adverse events, protocol deviations/violations, and unanticipated events will be reported to the IRBs with oversight of recruiting sites, the DSMB, and The National Cancer Institute.

9. Stopping Rules

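### Final SAP 7.b claims at least 80% power to exclude an interaction OR of 2.0, but its inputs give about 49%, or about 75% if the $0-arm OR is treated as known

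*Combined protocol and SAP*

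**What the plan says.** Final SAP 7.b bases the sample size of each embedded trial on excluding undue inducement, expressed as an interaction OR of 2.0 or more between incentive and risk perception. The calculation is simplified: "To facilitate such a power estimation, we considered groups of participants with greater or less than the median level of risk perception", with the highest incentive compared with the lowest. On the cell sizes it says that "96 participants will be assigned to each of the 3 incentives within both the high and low risk-perception groups". For the $0 arm, "we set the OR contrasting the odds of enrollment between riskperception groups to 1", so that the OR in the highest-incentive arm stands for the interaction. It takes a true interaction OR of 1 and says it will "use a one-sided significance level of 0.0427". Its conclusion is: "If the enrollment rate in the parent trials is 50%, we will have at least 80% power to rule out undue inducement".

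Two sentences extend the claim. One says that "because we will actually analyze risk as a continuous variable and incentive size as a 3-level variable, our true power will be greater" than the figures given. The other covers the income and economic well-being tests: "Similar analyses suggest similar levels of power to rule out the unjust inducement interaction terms".

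Elsewhere, section 5.c sets one-sided alpha at 0.05, treats incentive as ordered, and gives the 2.0 margin without a unit of risk or incentive. The Final Protocol abstract says that power to rule out these interactions is adequate, without a figure. The 17 February 2020 entry in the SAP change log reports that, at interim, more than 85% of risk scores in the Ambulation trial (apparently MOVE IT) were 0, and that scores in the smoking trial were extremely right skewed.

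**The concern.** Every input to the power figure is stated, so it can be checked directly. An interaction OR is a ratio of two ORs, each estimated from two cells, and four cells of 96 look too few to exclude 2.0 with 80% power.

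The figure matters because 576 per trial rests on it, and because these interactions address Aim I, the trial's primary aim. If a final analysis fails to exclude 2.0, readers will set that result against a claimed 80% power. If the real power of the stated contrast is near one half, failing to exclude 2.0 is about as likely as not even when there is no interaction at all.

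**Working it through.** **Inputs (Final SAP 7.b unless noted).** 576 per trial; 192 per arm; 96 per arm-by-risk cell; 50% enrolment; true interaction OR 1; margin 2.0; one-sided alpha 0.0427. Section 5.c gives alpha 0.05, used here as a variant.

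**Formula.** Power = Φ(ln 2 / SE − z), with ln 2 = 0.693, z(0.0427) = 1.720 and z(0.05) = 1.645. Each cell contributes variance 1/(96 × 0.5 × 0.5) = 1/24 to the log OR.

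**Stated contrast, 96 per cell**

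| | Four cells (both ORs estimated) | Two cells ($0-arm OR treated as known) |
|---|---|---|
| SE | √(4/24) = 0.408 | √(2/24) = 0.289 |
| Power at 0.0427 | Φ(1.698 − 1.720) = 49% | Φ(2.401 − 1.720) = 75% |
| Power at 0.05 | 52% | 78% |
| Simulated power, 1,000,000 runs (0.0427; 0.05) | 48%; 52% | 74%; 78% |
| Margin with 80% power, exp[SE × (z + 0.842)] | 2.85 (2.76 at 0.05) | 2.09 (2.05 at 0.05) |
| Needed per cell for 80% at 2.0 | 16 × (2.562/0.693)² → 219 (206 at 0.05) | 8 × (2.562/0.693)² → 110 (103 at 0.05) |
| Total over six cells | 1,314 (1,236) | 660 (618) |

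**Attempts to reproduce 80%.** Two-proportion versions of the two-cell case give 72% to 75% at 0.0427 and 75% to 77% at 0.05. A three-arm linear trend, with the margin taken as highest versus lowest, gives 49% to 50% at 0.0427. Fifty per cent enrolment is the most favourable rate; at 40% the four-cell and two-cell figures are 47.7% and 73.6%. With the $0-arm OR treated as known, changing a stated input does pass 80%: doubling alpha to 0.0854 gives 84.9%, and 192 per cell gives 95.3%.

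**Planned model (continuous risk, three equally spaced arms).** In large samples at 50% enrolment, with arm scores 0, 1, 2 (variance 2/3), the SE per incentive step is √(1/(576 × 0.25 × 2/3))/SD = 0.102/SD. Highest versus lowest it is 0.204/SD. SD is the standard deviation of the risk score in the risk unit of the margin. For 80% power at 2.0 and alpha 0.0427 the SE must be 0.693/2.562 = 0.271, so the SD must be at least:

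- 0.204/0.271 = 0.75 units if the margin is highest versus lowest;
- 0.102/0.271 = 0.38 units if it is per step.

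With one SD as the unit, power is 95% highest versus lowest and above 99.9% per step. With an even binary split (SD 0.5) it is 49% highest versus lowest and 95% per step.

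**Effect of the observed scores.** With more than 85% of scores at 0, the median is 0 and a 96/96 split cannot be formed in the Ambulation trial. For the secondary 0 versus >0 analysis there, at most 15% are above 0, so SD ≤ √(0.15 × 0.85) = 0.357. Highest versus lowest, SE ≥ 0.204/0.357 = 0.572 and power is at most about 31% at 0.0427 (33% at 0.05). If 10% are above 0, it is about 24% (27%). If the margin is per step, SE ≥ 0.286 and power is at most about 76% at 0.0427.

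**The case against.** The strongest reply is that 7.b describes a two-cell calculation: it fixes the $0-arm OR at 1 and puts the confidence limit on the OR in the highest-incentive arm. Judged by that method, the miss is about 5 points at 0.0427 and about 2 at 0.05. The fall to 49% then criticises the method rather than the sum. This is a fair reading, and both figures should be shown. But fixing the true $0-arm OR is only an assumption about its value. The trial must still estimate it from 192 people, and the planned interaction test carries that error. Even 75% is not at least 80%.

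A second reply is that the median split is only a planning device and that the planned model could have 95% power or more. That is true for some units of the margin, so the trial has not been shown to be underpowered. It does not rescue the statement, because the 80% is attached to the split contrast and the claim of greater power cannot be checked without a unit.

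Three smaller points stand. The skewed scores were seen after 576 was set, so they are not a planning error. The SAP claims no power for the 0 versus >0 analysis. The abstract speaks only of adequate power and does not repeat 80%.

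**Conclusion.** The stated power is wrong on either reading of 7.b. For the contrast described, 576 per trial gives about 49% power to exclude an interaction OR of 2.0, or about 75% if sampling error in the $0 arm is ignored. Changing alpha to 0.05 does not bring either to 80%. These figures need only the inputs stated in 7.b and a Wald test on the log-OR scale, which simulation supports.

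Power for the planned model is undetermined. The figures shown for it assume equally spaced arms and a chosen unit, and they fall on both sides of 80%. Applying the observed scores to MOVE IT assumes that it is the Ambulation trial.

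The consequence is limited to the sample-size justification, its extension to the unjust-inducement tests, and the reading of an inconclusive result. The chance of wrongly excluding inducement is not increased by this error.

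**What to change.** 1. Restate 7.b along these lines: for the highest-versus-lowest, median-split contrast (96 per cell, 50% enrolment, true interaction OR 1), 576 per trial gives about 49% power at one-sided 0.0427 (52% at 0.05) to exclude an interaction OR of 2.0, and 80% power to exclude about 2.85 (2.76 at 0.05). If the two-cell figure of 75% is kept beside it, say that it ignores sampling error in the $0 arm.
2. In 5.c, state the unit of risk and of incentive (per step, or highest versus lowest) to which 2.0 applies, and fix it before the final interaction models are run. Power depends heavily on this choice and interim scores have been seen, so give a subject-matter reason for the unit. If the models have already been run, say so.
3. Delete the sentence that true power will be greater, or replace it with a figure for the chosen unit, computed from the observed scores pooled over arms rather than from an assumed normal score.
4. Note in 7.b that the 96/96 split cannot be formed in the Ambulation trial. Note also that 576 was not sized for the secondary 0 versus >0 analysis there, which has at most about 31% power at 0.0427 highest versus lowest (about 76% if the margin is per step).
5. Use one final alpha in 5.c and 7.b, and carry the restated power into the protocol abstract.

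The cost is SAP wording and one sentence in the abstract, with no extra patients. The stated power becomes less favourable, and the sponsor must commit to a unit for the margin.

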	secondary	risk score distributions. We found that in the Ambulation trial the
	analysis of the	risk score mostly (>85%) clumped on 0, and in the smoking trial the
	risk score and	score is extremely right skewed. To better handle this sparsity of
	incentives where	data we planned a secondary analysis in which we treat the risk
	risk score is	scores as binary and compare the inferences.
	treated as a	
	binary variable (0	
	and >0).	

VI. Final Statiscal Analysis Plan

1. Background and rationale

This study is designed to provide the first-ever real-world tests of a broad range of intended and unintended consequences of financial incentives for research participation. It will do so through the conduct of two separate, but similarly designed, embedded randomized trials within actual parent clinical trials. It is our hope the findings from this study will inform research regulations and guide the use of incentives in future RCTs so as to expedite medical innovation and improve health

2. Objectives and hypotheses

The aims of this study are to (1) determine if the ethical concerns with incentives for research participation actually manifest; and (2) assess the possible scientific and ethical benefits of financial incentives for RCT participation.

We hypothesize that research incentives will:

- Augment participants' perceptions of risk without disproportionately encouraging economically disadvantaged participants to enroll
- Demonstrate an increased enrollment fraction in the parent trials, thereby enhancing the scientific value and validity of the research by augmenting the precision of the studies

3. Design and randomization

RETAIN comprises two prospective randomized controlled trials, embedded within two parent trials conducted in parallel, each comparing three intervention arms. Arms vary by the amount of the financial incentives that are offered to potential participants. Amounts offered differ on a per trial basis determined by the relative time and effort being asked of the participant for each parent trial. Assignment to arms is determined by computerized random-number generation with block randomization using variable block sizes of 3 and 6. Participants in both embedded trials have a 33.3% probability of being assigned to each RETAIN arm.

a. BASC Trial

• The Behavioral Activation and Varenicline for Smoking Cessation in Depressed Smokers Study (BASC) (NCT 02378714)

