the outcome of enrollment in the parent trials. We will test two interactions, each in a separate model to avoid collinearity, to determine if incentives represent unjust inducements: that between incentive size and the primary covariate of annual household income, and that between incentive size and the primary covariate of economic well-being. All analyses will be stratified by parent study.

Analyses of interaction terms will be structured as tests of non-inferiority. The null hypothesis, for both trials, will be that the use of incentives meets criteria for undue or unjust inducement. We can reject the null, and conclude the absence of undue or unjust inducement, if the interaction terms are "small" according to pre-specified criteria (in technical terms, the inferiority margin). Said a different way, our analyses are designed to determine if we can exclude the possibility that incentives represent undue or unjust inducements if the resulting interaction terms are sufficiently small. Specifically, we will use one-sided alpha levels of 0.05 to exclude, with 95% confidence, the possibility that any of these interaction odds ratios are >2.0.

We will explore temporal trends in incentives' effects over the study period using stratified analyses. If temporal trends are noted, as may occur if prospective patients learn of the incentives used in these studies, we will adjust for their influence by entering time as a covariate, modeled as a spline. We will evaluate potential effect modifiers (variables in Table 1) using stratified analyses. If differences among strata appear, we will formally test their corresponding interactions with the incentive amount.

TABLE 1 FACTORS FOR ADJUSTMENT AND EXPLORATION OF EFFECT MODIFICATION

Potential factors for adjustment			
Patient level covariates	Variable coding or definition		
• Age	Continuous		
• Gender	Binary		
• Race	Categorical		
Marital status	Categorical		
Education	Categorical		
Income	Categorical		
Economic well-being	Categorical		
Prior research participation	Categorical		
Attitudes towards research:	Continuous, measured using the Research Attitudes Questionnaire-7 (RAQ- 7).		

6. Secondary analysis

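### Final SAP 7.b claims that true power exceeds the stated 80%, but three incentive levels add about one point at most at 50% enrolment and MOVE IT's risk scores rule out the assumed median split

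*Combined protocol and SAP*

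**What the plan says.** Final SAP 7.b sizes each sub-trial at 576, or 192 per arm. It splits each arm at the median risk perception into 96 above and 96 below, and compares the highest with the lowest incentive. The true interaction OR is taken as 1, the OR in the $0 arm is set to 1, and the plan will "use a one-sided significance level of 0.0427". The result is: "If the enrollment rate in the parent trials is 50%, we will have at least 80% power to rule out undue inducement", with 2.0 as the margin.

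Two closing statements follow. The first is that, with risk analysed as continuous and "incentive size as a 3-level variable, our true power will be greater than the estimates reported here". The second is "Similar analyses suggest similar levels of power to rule out the unjust inducement interaction terms".

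Four other places bear on these statements:
- Final SAP 5.c treats incentive as an ordered variable and aims to exclude "the possibility that any of these interaction odds ratios are >2.0". It gives no unit for the odds ratio, either for incentive or for risk.
- The change log (section V, entry of 2/17/2020) says that in the Ambulation trial the "risk score mostly (>85%) clumped on 0, and in the smoking trial the" score is extremely right skewed. Only two sub-trials remain and the other is the smoking trial, so Ambulation is read here as MOVE IT.
- Final SAP section 6 responds with a secondary analysis of risk as 0 versus >0.
- Final SAP section 9 defines unjust inducement as an interaction with income or with economic well-being.

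The power text in 7.b is the same as in section 8.b of the Original SAP.

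**The concern.** The first closing statement turns 80% into a lower bound for both trials. Its two reasons are the number of incentive levels and the continuous risk score. A middle arm contributes little to a slope fixed by its two ends. The gain from a continuous score depends on spread, and the change log reports that spread is largely missing.

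The final analysis is a non-inferiority test. Failing to exclude 2.0 can mean either that an interaction exists or that the data carry too little information. A reader told that power exceeds 80% will lean towards the first explanation. In MOVE IT the second may be the right one.

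The second closing statement gives power for the unjust-inducement terms without saying that concluding absence requires both terms to be excluded.

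**Working it through.** **Formula.** Wald test on the log interaction OR, true OR 1: power = Φ(ln 2 / SE − z). Here ln 2 = 0.693 and z = 1.720 for one-sided 0.0427. Enrolment is 50% unless stated, so each person carries variance weight 0.5 × 0.5 = 0.25.

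**Step 1. The plan's own figure.**
- Four cells of 96 (a true interaction): SE = √(4 / (96 × 0.25)) = 0.408; power = Φ(1.698 − 1.720) = 49.1%.
- Two cells of 96, with the $0-arm OR treated as known: SE = √(2 / (96 × 0.25)) = 0.289; power 75.2%.
- At one-sided 0.05, the level in 5.c ("we will use one-sided alpha levels of 0.05 to exclude"), these become 52.1% and 77.5%.

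Neither formula reproduces 80%. That is a separate matter. The figures serve here only as baselines for measuring change.

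**Step 2. What three levels add.** With equal arms, the variance of the end-to-end contrast from an ordered slope is proportional to (x3 − x1)² / Σ(x − mean)². For two arms alone it is 2.

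| Incentive scores | Variance factor | Power (from 49.1%) | Power (from 75.2%) |
|---|---|---|---|
| Equally spaced | 2.000 | 49.1% | 75.2% |
| BASC dollars, 0/200/500 | 1.974 (−1.3%) | 49.6% | 75.7% |
| MOVE IT dollars, 0/100/300 | 1.929 (−3.6%) | 50.4% | 76.6% |

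The gain from the true-interaction baseline is 0 to 1.3 points.

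**Step 3. What continuous risk could add.** Assume a roughly normal score. The two halves of a median split then differ by 1.596 SD in mean, so the equivalent margin is ln 2 / 1.596 per SD. The SE per SD is √(2 / (192 × 0.25)) = 0.204. Power rises from 49% to 66%. This half of the argument is sound for a well-spread score.

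**Step 4. MOVE IT with 85% zeros.** The median is 0 and nobody lies below it, so 96/96 cannot be formed. For the secondary 0 versus >0 contrast, SE = √(2 × (1/(n₁ × 0.25) + 1/(n₂ × 0.25))):
- 85/15 (163.2 and 28.8 per arm): SE 0.572, power 31%.
- 90/10 (172.8 and 19.2 per arm): SE 0.680, power 24%.
- With the $0-arm OR treated as known: 50% and 39%.

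Because the log says over 85%, 31% is an upper figure for this contrast under these assumptions.

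**Step 5. MOVE IT, primary continuous model.** Assume a margin of 2.0 per risk point, end to end in incentive, with equally spaced incentive scores. Then SE = √(2 / (192 × 0.25 × Var(risk))). The spreads below are assumptions, because the documents give none.

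| Non-zero scores (15% in total) | Var(risk) | SE | Power |
|---|---|---|---|
| All equal to 1 | 0.1275 | 0.572 | 31% |
| 1 (10%), 2 (5%) | 0.26 | 0.400 | 50% |
| 1, 2, 3 (5% each) | 0.61 | 0.261 | 82% |

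A wider spread goes higher still.

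**Step 6. Unjust inducement.** If each term has 80% power, the probability that both are excluded is 0.8² = 64% when independent. From the bivariate normal it is 71% at correlation 0.7 and 75% at 0.9. It reaches 80% only under perfect correlation. The correlations are assumptions.

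**The case against.** The strongest reply is that the sentence in 7.b rests on two reasons, and continuous risk is a legitimate one. That stands: step 3 shows a real gain for a well-spread score. A reader might therefore infer from step 2 that the sentence is shown false for both trials. The documents do not support that. For BASC they report skew but no distribution from which to compute.

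A reader might also take 31% as MOVE IT's power. It is not. The 0 versus >0 coding is a secondary analysis, and the primary model is continuous. Step 5 runs from 31% to 82% under assumed spreads.

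The unit of the margin matters too. If 2.0 applied per ordered incentive step (4.0 end to end), the 85/15 contrast would have about 76% power. Section 7.b computes highest against lowest, which supports the end-to-end reading, but 5.c does not say so.

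Nor is step 2 a general cap on what a third level can add. With enrolment of 20/30/40% by arm, MOVE IT dollar scores raise power from 40.8% to 43.7%, about 3 points.

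On unjust inducement, 7.b refers to terms in the plural and is naturally read as per-term power. It does not claim that one test is enough. Joint power is missing rather than misstated.

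Finally, 7.b was written before BASC and MOVE IT enrolment, and the clumping was learned at the interim analyses. The change log discloses it, and the plan adds influence diagnostics and the binary analysis. What remains is that the Final SAP kept the power paragraph unrevised after recording facts that remove its basis.

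**Conclusion.** The statement that true power will exceed 80% is unsupported and should not stand. On an end-to-end OR at 50% enrolment, three ordered levels add 0 to 1.3 points. The continuous-risk reason needs spread that the change log does not show: over 85% zeros in MOVE IT and extreme right skew in BASC. The 96/96 split cannot exist in MOVE IT, so 80% is not a floor there.

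Power for the 0 versus >0 contrast is about 31% at 85/15 and 24% at 90/10 (50% enrolment, one-sided 0.0427, end-to-end OR 2.0). Power for the primary continuous model cannot be fixed from the documents. It may lie well below or somewhat above 80%, depending on the non-zero scores and the unit of the margin. The unjust-inducement sentence omits the joint probability, which is 64% to 75% for correlations of 0 to 0.9 if each term has 80%.

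These results rest on a Wald approximation, a true interaction OR of 1, equal arms, and the reading of Ambulation as MOVE IT.

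**What to change.** In Final SAP 7.b:
1. Delete the sentence claiming greater true power.
2. State that the 2.0 margin is for highest versus lowest incentive, and per which unit of risk. Repeat this in 5.c.
3. Replace the MOVE IT figure with power computed from the observed risk distribution for the primary continuous model. Give the secondary 0 versus >0 contrast separately (about 31% at 85/15, 24% at 90/10, with the assumptions named).
4. State that the unjust-inducement power is per term and that excluding both is less likely: 64% if independent and 75% at correlation 0.9, given 80% each, with the correlations labelled as assumptions.

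The cost is SAP wording and one recalculation from data the team already holds. No change to design, conduct or sample size is needed. The plan gives up its stated floor, and some published figures may become less favourable.
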